2 SAFETY ASSESSMENTS

Safety assessments (medical/surgery history, demographics, prior and concomitant medications, vital signs, physical examinations, ECGs, clinical laboratory assessments, and AEs) are to be performed at the visits specified in the Schedule of Assessments (Table 1).

121 Medical/Surgical History and Demographics

Medical/surgical history will be recorded at screening. Investigators will document all active and chronic diseases (eg, asthma and COPD), and any diseases diagnosed in the past 1 year (before

This document is confidential.

Page 58 of 89
MetrioPharm AG
MP1032

screening) that the investigator considers clinically significant. Additional pre-existing conditions present at the time when informed consent is given and up to the time of first dosing (Day 1) are to be regarded as concomitant. Medical history will include documentation of social behaviors, including use of tobacco, nicotine (including use of electronic cigarettes), and soft or hard drugs (including cannabis), as well as alcohol consumption, if applicable. Smoking history also must be documented as part of medical history and includes never, light (<100 cigarettes/lifetime), active smoker, and former smoker (quit date). History of number packs/day, number of smoking years, and quitting time for former and active smokers must also be documented.

Additionally, the investigators will document at screening the patient's Charlson score via the Charlson Comorbidity Index (Charlson et al 1987) (Appendix 1). The Charlson Comorbidity Index may be used to identify patients with higher risk of COVID-19 progression (Garibaldi et al 2020) via the COVID-19 Inpatient Risk Calculator (online calculator available via: https://rsconnect.biostat.jhsph.edu/covid_predict/). The 14-item Charlson score is based on the patient's comorbidities that are associated with mortality: myocardial infarction, congestive heart failure, peripheral vascular disease, cerebrovascular disease, dementia, chronic pulmonary disease, rheumatologic disease, peptic ulcer disease, liver disease, diabetes, hemiplegia or paraplegia, renal disease, malignancy, and acquired immunodeficiency syndrome/human immunodeficiency virus (online calculator available via: https://www.orthotoolkit.com/charlson-comorbidity-index/). The investigator should record each individual component of the 14-item Charlson Comorbidity Index (Appendix 1) as well as the overall score.

Illnesses first occurring or detected during the study and/or worsening of a concomitant illness during the study are to be documented as AEs on the eCRF in accordance with Section 12.6.1. All changes not present at baseline or described in the past medical history and identified as clinically noteworthy must be recorded as AEs.

Additionally, demographic data will be collected for all patients and include sex, age, and race and/or ethnicity.

12.2 Vital Signs

Vital signs (systolic and diastolic blood pressure, heart rate, respiration rate, SpO₂, and body temperature) will be evaluated at the visits indicated in the Schedule of Assessments (Table 1). All vital signs will be measured after the patient has been resting for at least 5 minutes. Blood pressure measurements are to be taken in the same arm for the duration of the study. Moreover, additional vital signs may be performed as needed in case of any cardiac AE.

Additionally, body weight (without shoes) will be recorded at screening, Day 1, Day 14, Day 28, Day 60, and day of discharge (applicable); height (without shoes) will be recorded at screening only. Body mass index will be calculated whenever weight is recorded.

Vital sign measurements will be repeated if clinically significant or machine/equipment errors occur. Out-of-range blood pressure, respiratory rate, heart rate measurements, or SpO₂ will be

This document is confidential.

Page 59 of 89

repeated at the investigator's discretion. Any confirmed, clinically significant vital sign measurements must be recorded as AEs.

12.3 Physical Examinations

MP1032

A complete physical examination will be performed at screening. Physical examinations will be performed by a physician. The complete physical examination includes head, eyes, ears, nose, and throat; heart; lungs; abdomen; skin; cervical and axillary lymph nodes; and neurological and musculoskeletal systems.

A limited physical examination to verify continued patient eligibility and to follow-up regarding any change in medical history will be performed at the visits indicated in the Schedule of Assessments (Table 1). Symptom-driven, limited physical examinations may be performed as clinically indicated during the study (according to SoC).

Please note: The limited physical examination on Day 8 (\pm 3 days) will be collected in all patients who remain hospitalized. If the patient is discharged before Day 8 (\pm 3 days), these assessments should only be done if the physician determines during the outpatient visit (ie, at the study site) that the limited physical examination is clinically indicated.

12.4 Electrocardiograms

A 12-lead, resting ECG will be obtained locally at screening as indicated in the Schedule of Assessments (Table 1). At screening, the investigator must examine the ECG traces for clinically significant abnormalities that could exclude the patient from the study. If ECGs are performed at unscheduled time points (eg, according to SoC), findings must be recorded in the eCRF.

ECGs should always be obtained in supine position after adequate rest (\geq 5 minutes). An assessment of normal or abnormal will be recorded; if the ECG is considered abnormal, the abnormality will be documented on the eCRF. ECGs will be repeated if clinically significant abnormalities are observed or artifacts are present. Any ECG considered by the investigator to be clinically significant should be considered an AE. Moreover, additional ECGs may be obtained as needed in case of any cardiac AE and will be recorded on the eCRF.

2.5 Clinical Laboratory Assessments

Clinical laboratory assessment samples (Table 5) will be obtained at designated visits as specified in the Schedule of Assessments (Table 1).

This document is confidential.

Page 60 of 89

Protocol v2.0 - Bulgaria

MP1032-CT05 Protocol v2.0 - Bulgaria

Hematology	Blood Biochemistry	Urinalysis (Dipstick)
Full and differential blood count	Albumin (ALB)	Appearance
Hematocrit (HCT)	Alanine aminotransferase (ALT)	pH
Hemoglobin (Hb)	Alkaline phosphatase (ALP)	Protein
Mean corpuscular hemoglobin (MCH)	Aspartate aminotransferase (AST)	Glucose
Mean corpuscular hemoglobin	Blood urea nitrogen (BUN) or urea	Ketone bodies
concentration (MCHC)	Carbon dioxide (CO_2)	Indicators of blood and
Mean corpuscular volume (MCV)	Creatinine ^a (Cr)	white blood cells
Platelet count (PLT Ct)	Creatine kinase (CK) and subtypes	Specific gravity
Red blood cell count (RBC ct)	Electrolytes (sodium, potassium,	Urobilinogen (UROB)
White blood cell count (WBC ct) with	chloride, calcium, phosphorus)	
differential	Gamma-glutamyl transpeptidase (GGT)	
	Glucose	
	Lactate dehydrogenase (LDH)	
	Total bilirubin (TBIL)	
	Direct bilirubin (DBI)	
	Total cholesterol (TC)	
	Triglycerides (TG)	
	Estimated glomerular filtration rate ^b	
	(eGFR)	
Coagulation		
Activated partial thromboplastin time		
International normalized ratio		
Partial thromboplastin time		
Pregnancy Test		
test will be performed on all WOCBP of be repeated on Day 14 (\pm 7 days). If the discharge should be done, and urine pro Day 14, urine pregnancy test should be	erformed on all WOCBP at screening and a on Day 1 before randomization and dosing. e patient is discharged before Day 14, uring egnancy test at Day 14 is not required. If the done at Day 14, and urine pregnancy test and nts with a positive pregnancy test will be d	A urine pregnancy test will e pregnancy test at day of he patient is discharged afte at day of discharge is not
Please note: In questionable cases of pos	stmenopausal status, a blood sample with s ls may be required to determine postmenop	
bbreviations: hCG = human chorionic g	onadotropin; WOCBP = women of childbe	aring potential.
Creatinine clearance will be estimated us	sing the patient's serum creatinine value, ad	
appropriate Cockroft-Gault formula f	or the patient's sex. pidemiology Collaboration (Levey et al 20	

Table 5: **Clinical Laboratory Assessments**

^b According to Chronic Kidney Disease Epidemiology Collaboration (Levey et al 2009).

Blood and urine samples will be analyzed at the site's local laboratory facility. Urine samples will be analyzed by dipstick, and a microscopic analysis will be performed if the results of dipstick indicate abnormalities to be further investigated. All laboratory reports must be reviewed, signed, and dated by the investigator. A legible copy of all reports must be filed with both the patient's eCRF and medical record (source document) for that visit. Any laboratory test result considered by the investigator to be clinically significant should be considered an AE (clinically significant AEs include those that require an intervention). Clinically significant

This document is confidential.

Page 61 of 89

abnormal values occurring during the study will be followed up until repeat test results return to normal, stabilize, or are no longer clinically significant. If laboratory assessments are performed at unscheduled time points (eg, according to SoC), findings must be recorded in the eCRF.

Please note: The clinical laboratory assessments on Day 8 (\pm 3 days) and Day 21 (\pm 2 days) will be collected in all patients who remain hospitalized. If the patient is discharged before Day 8 (\pm 3 days) or Day 21 (\pm 2 days), the physician should assess the patient at the outpatient visit (ie, at the study site). If the physician determines during the outpatient visit (ie, at the study site) that the clinical laboratory assessments are clinically indicated, then the site should arrange to collect this assessment.

12.6 Adverse Events

12.6.1 Adverse Events

An AE is any symptom, physical sign, syndrome, or disease that either emerges during the study or, if present at screening, worsens during the study, regardless of the suspected cause of the event. All medical and psychiatric conditions (except those related to the indication under study) present at screening will be documented on the medical history eCRF. Changes in these conditions and new symptoms, physical signs, syndromes, or diseases should be noted on the AE eCRF during the rest of the study. Clinically significant laboratory abnormalities should also be recorded as AEs. Surgical procedures that were planned before the patient was randomized in the study are not considered AEs if the conditions were known before study inclusion; the medical condition should be reported in the patient's medical history.

Patients will be instructed to report AEs at each study visit. All AEs are to be followed up until resolution or a stable clinical endpoint is reached.

Each AE is to be documented on the eCRF with reference to date of onset, duration, frequency, severity, relationship to study drug, action taken with study drug, treatment of event, and outcome. Furthermore, each AE is to be classified as being serious or nonserious. Changes in AEs and resolution dates are to be documented on the eCRF.

For the purposes of this study, the period of observation for collection of AEs extends from the time the patient gives informed consent until the end of the follow-up period (Day 60). Follow-up of the AE, even after the date of study completion, is required (if possible) if the AE persists. The follow-up should continue until the event resolves (returns to normal or baseline values) or stabilizes, or until it is judged by the investigator to no longer be clinically significant. It is understood that if a patient withdraws consent to further follow-up, then it may not be possible for the study site to follow the AE to resolution.

When changes in the severity of an AE occur more frequently than once a day, the maximum severity for the event should be noted. If the severity category changes over a number of days, then those changes should be recorded separately (with distinct onset dates).

MetrioPharm AG	MP1032-CT05
MP1032	Protocol v2.0 - Bulgaria

Each AE will be assigned a grade which refers to the severity of the AE based on the Common Terminology Criteria for Adverse Events version 5.0. The Common Terminology Criteria for Adverse Events v5.0 displays grades 1 through 5 with unique clinical descriptions of the severity for each AE based on the general guideline shown in Table 6.

The guideline for classifying AEs by relationship to study drug are given in Table 7.

Table 6: Classification of Adverse Events by Severity

Grade 1: Mild; asymptomatic or mild symptoms; clinical or diagnostic observations only; intervention not indicated.

Grade 2: Moderate; minimal, local or non-invasive intervention indicated; limiting age-appropriate instrumental activities of daily living.

Grade 3: Severe or medically significant but not immediately life-threatening; hospitalization or prolongation of hospitalization indicated; disabling; limiting self-care activities of daily living.

Grade 4: Life-threatening consequences; urgent intervention indicated.

Grade 5: Death related to AE.

Abbreviation: AE = adverse event.

MetrioPharm AG	MP1032-CT05
MP1032	Protocol v2.0 - Bulgaria

Table 7: Classification of Adverse Events by Relationship to Study Drug

UNRELATED: This category applies to those AEs that are clearly and incontrovertibly due to extraneous causes (disease, environment, etc).

UNLIKELY: This category applies to those AEs that are judged to be unrelated to the study drug but for which no extraneous cause may be found. An AE may be considered unlikely to be related to study drug if or when it meets 2 of the following criteria: (1) it does not follow a reasonable temporal sequence from administration of the study drug; (2) it could readily have been produced by the patient's clinical state, environmental or toxic factors, or other modes of therapy administered to the patient; (3) it does not follow a known pattern of response to the study drug; or (4) it does not reappear or worsen when the drug is readministered.

POSSIBLY: This category applies to those AEs for which a connection with the study drug administration appears unlikely but cannot be ruled out with certainty. An AE may be considered possibly related if or when it meets 2 of the following criteria: (1) it follows a reasonable temporal sequence from administration of the drug; (2) it could not readily have been produced by the patient's clinical state, environmental or toxic factors, or other modes of therapy administered to the patient; or (3) it follows a known pattern of response to the study drug.

PROBABLY: This category applies to those AEs that the investigator feels with a high degree of certainty are related to the study drug. An AE may be considered probably related if or when it meets 3 of the following criteria: (1) it follows a reasonable temporal sequence from administration of the drug; (2) it could not be reasonably explained by the known characteristics of the patient's clinical state, environmental or toxic factors, or other modes of therapy administered to the patient; (3) it disappears or decreases on cessation or reduction in dose (note that there are exceptions when an AE does not disappear upon discontinuation of the drug, yet drug-relatedness clearly exists; for example, as in bone marrow depression, fixed drug eruptions, or tardive dyskinesia); or (4) it follows a known pattern of response to the study drug.

DEFINITELY: This category applies to those AEs that the investigator feels are incontrovertibly related to study drug. An AE may be assigned an attribution of definitely related if or when it meets all of the following criteria: (1) it follows a reasonable temporal sequence from administration of the drug; (2) it could not be reasonably explained by the known characteristics of the patient's clinical state, environmental or toxic factors, or other modes of therapy administered to the patient; (3) it disappears or decreases on cessation or reduction in dose and recurs with reexposure to drug (if rechallenge occurs); and (4) it follows a known pattern of response to the study drug.

Abbreviation: AE = adverse event.

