12.6.4 Suspected Unexpected Serious Adverse Reactions

AEs that meet all of the following criteria will be classified as suspected unexpected serious adverse reactions (SUSARs) and reported to the appropriate regulatory authorities in accordance with applicable regulatory requirements for expedited reporting:

- serious
- unexpected (ie, the event is not consistent with the reference safety information in the current version of the IB)
- there is at least a reasonable possibility that there is a causal relationship between the event and the study drug

The investigator will assess whether an event is causally related to the study drug. Syneos Health will consider the investigator's assessment and determine whether the event meets the criteria for being reportable as a 7-day or 15-day safety report. SUSARs that are fatal or life-threatening must be reported to the regulatory authorities and the IRBs/IECs (where required) within 7 days after Syneos Health/MetrioPharm has first knowledge of them, with a follow-up report (when applicable) submitted within a further 8 calendar days. Other SUSARs must be reported to the relevant regulatory authorities and the IRBs/IECs within 15 calendar days after Syneos Health/MetrioPharm first has knowledge of them.

Syneos Health is responsible for reporting SUSARs and any other events required to be reported in an expedited manner to the regulatory authorities and for informing investigators of reportable events, in compliance with applicable regulatory requirements within specific timeframes. Investigators will notify the relevant IRBs/IECs of reportable events within the applicable timeframes.

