15.8 Data Monitoring Committee

An independent DMC will be established by the sponsor or designee to review accumulating study data at regular intervals (as per the DMC charter) throughout the study to ensure the safety of patients and review overall study conduct. Additional data may be reviewed that are related to efficacy, but the DMC will only be reviewing data for risk-benefit purposes. Members will include experts in drug safety and/or medical specialist and biostatistics, who are not participating in this study and do not have affiliation with the investigators or the sponsor. The DMC can recommend in writing to the sponsor whether to continue, modify, or stop the clinical study on the basis of safety considerations. The pre-specified study stopping rules for the trial are defined as follows:

- death (not including disease progression) in any patient in whom the cause of death is judged to be related to the study drug by investigator
- the occurrence in any patient of a SAE whose causal relationship (ie, without a plausible alternative explanation) to the study drug is judged to be related by investigator
- two occurrences of a clinically significant Grade 3 or higher laboratory abnormality assessed to be related to the study drug by investigator.

The DMC's specific duties will be fully described in a DMC charter.

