5.2.1 Nonclinical Studies

In vivo safety studies showed no evidence of neurotoxic potential or negative cardiohemodynamic effects; no local intolerance was observed. There was no dose-limiting or target organ toxicity and no substance-related findings in histopathology in rats or dogs. However, after 6 months of long-term treatment in rats receiving the highest dose (1000 mg/kg/d), liver organ weight was elevated compared with that of controls and histopathologically associated with hepatocellular hypertrophy. This finding was not considered adverse because of its adaptive character, as histopathological changes were not present at the end of the recovery period (ie, effect was reversible after 8 weeks).

In reproduction toxicity studies on fertility, early embryonic, and embryo-fetal development, no pathological effects were found. On the basis of results from 4 different test systems, mutagenic or clastogenic effects are not considered to be a potential risk for volunteers and patients.

Transient effects on some pulmonary parameters have been observed in rats following a single intravenous bolus injection of the highest dose (300 mg/kg) of MP1032. No pulmonary effects have been observed in any of the long-term animal toxicity studies. The maximum plasma levels reached in humans are over 1000 times (oral) lower than for the abovementioned dose. Thus, pulmonary effects are not considered a potential risk for patients and volunteers.

Emesis sporadically occurred in various repeat-dose toxicology studies in dogs; the emesis was present in the dogs more often at the high doses of 150 mg/kg twice daily (BID) intravenous than at 125 mg/kg BID (oral). The lowest experimental oral dose inducing emesis was 25 mg/kg BID

This document is confidential.

Page 26 of 80

MetrioPharm AG	MP1032-CT05
MP1032	Protocol v2.0 - France

(oral) in dogs, corresponding to 1.8 g (oral; conversion based on human-equivalent dose) for a 65-kg human. Dogs are well known to be susceptible to emesis; in addition, the maximum doses administered in humans are 6 to 30 times below the converted human-equivalent doses. Therefore, emesis is not considered a potential risk for patients and volunteers.

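### Table 7's causality criteria contradict their own descriptions and steer a new, well-timed event with a possible alternative cause to unlikely, a stricter test than the SUSAR section sets

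*Protocol*

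**What the plan says.** Section 12.6.1, in both the Bulgarian and the French protocol, offers Table 7 as the guideline for grading relationship to study drug. Two grades matter here.

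- **Unlikely.** The description covers events thought not to come from the drug, but for which no outside cause can be identified. The rule follows: "An AE may be considered unlikely to be related to study drug if or when it meets 2 of the following criteria". The four criteria are unreasonable timing; "it could readily have been produced by the patient's clinical state, environmental or toxic factors, or other modes of therapy administered to the patient"; no known pattern of response; and no reappearance or worsening on re-dosing.
- **Possibly.** The description covers a link that looks improbable but cannot be excluded for certain. The rule follows: "An AE may be considered possibly related if or when it meets 2 of the following criteria". The three criteria are reasonable timing; "it could not readily have been produced by the patient's clinical state" (nor by environment or other therapy); and a known pattern.

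Probably takes 3 of 4: timing, no reasonable alternative, improvement on stopping, known pattern. Definitely requires all of its criteria, a known pattern among them. No precedence between grades is given.

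Section 12.6.4 defines a SUSAR as serious, unexpected against the reference safety information, and such that "there is at least a reasonable possibility that there is a causal relationship between the event and the study drug". The investigator assesses causality; the contract research organisation considers that view and decides reportability. The three study stopping rules in Section 15.8 each turn on the investigator's judgement of relatedness. Rule 3, for example, is two occurrences of a "clinically significant Grade 3 or higher laboratory abnormality assessed to be related to the study drug by investigator". Neither section says which Table 7 grades amount to related.

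**The concern.** Each description says one thing and its criteria do another. Unlikely is meant for events with no outside cause, yet an outside cause that readily explains the event counts towards it. Possibly is meant for a link that cannot be excluded, yet an event with no known pattern cannot reach it on timing alone if the disease or another therapy might also explain it.

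The class of event affected is the one SUSAR reporting exists for. A SUSAR must be unexpected, and an unexpected event will usually lack a known pattern. Section 5.2.2 reports no serious adverse event in anyone given MP1032, so there is no observed human pattern for a serious reaction. All patients enter as inpatients with COVID-19 on standard of care, so a candidate alternative cause will often be available.

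At stake are the investigator's input to SUSAR decisions, stopping rules 1 and 3, and the treatment-related summaries in Section 15.4. Rule 3 deserves notice because a Grade 3 laboratory abnormality need not be serious, so the duty to report every SAE need not catch it.

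**Working it through.** The plan states no figure on this point. The check is to code Table 7 as yes/no judgements and count.

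**Inputs (Table 7).** T: timing is reasonable. E: disease, environment or other therapy could readily explain the event. K: it follows a known pattern. D: it improves on stopping. R: re-dosing is not done, negative (no reappearance or worsening) or positive. E is taken as the same judgement whether the table says readily produced or reasonably explained.

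**Formulas.**
- u = number true among {not T, E, not K}; p = number true among {T, not E, K}. These mirror each other, so p = 3 − u.
- Unlikely is met if u + r ≥ 2, where r = 1 only for a negative re-dosing.
- Possibly is met if p ≥ 2, that is, u ≤ 1.
- Probably is met if p + d ≥ 3, where d = 1 if the event improves on stopping.

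**Step 1: new, well-timed event with a ready alternative (T yes, E yes, K no).** u = 0 + 1 + 1 = 2 and p = 3 − 2 = 1. Unlikely is met whatever r is. Possibly fails (1 of 3). Probably fails, since p + d is at most 1 + 1 = 2. Definitely fails because K is no. D has 2 values and R has 3, so there are 2 × 3 = 6 combinations, and unlikely is the only grade in all 6. That includes improvement on stopping followed by recurrence on re-dosing. The unrelated grade does not apply, because it needs an outside cause that is certain, not merely available.

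**Step 2: what an event with no known pattern needs.** With K no and no re-dosing, u = (not T) + E + 1. It avoids unlikely only if u ≤ 1, so T must be yes and E must be no. Table 7 then asks for good timing and the absence of a ready alternative. Section 12.6.4 asks for at least a reasonable possibility, and an alternative explanation does not by itself rule that out. Table 7 is the stricter test.

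**Step 3: overlap of unlikely with possibly.** Both hold when u ≤ 1 and u + r ≥ 2, which requires u = 1 and r = 1. There are 3 ways to have u = 1. With T, E, K and negative re-dosing each coded yes/no there are 2⁴ = 16 combinations, and 3 overlap. In the fuller coding there are 2 × 2 × 2 × 2 × 3 = 48 combinations, and 3 × 2 = 6 overlap. In 3 of those 6 the event improved on stopping, so p + d = 2 + 1 = 3 and probably is met as well. Without re-dosing, none of the 16 combinations mixes unlikely with a higher grade. In total 18 of 48 combinations meet two or more grades; the remaining 18 − 6 = 12 are nested overlaps among possibly, probably and definitely.

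**The case against.** The strongest answer is that Table 7 is a guideline whose grades say an event may be considered to belong, so an investigator in doubt can rely on the description of possibly and choose it. That stands: nobody is compelled to grade such an event unlikely. It does not remove the contradiction, because an investigator who follows the listed criteria is pointed the other way.

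A known pattern is not confined to the clinical reactions listed in Section 5.2.2. Section 5.2.1 reports that in long-term treated rats "liver organ weight was elevated compared with that of controls", and creatinine rose in a mouse study. An investigator might count these as a pattern, in which case timing plus pattern gives possibly. Section 5.3 also promises case-by-case evaluation of suspected events arising from preclinical risks. So the argument should not rest on liver or kidney events; it concerns any event judged to have no known pattern.

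The safeguards are substantial. Every SAE is reported within 24 hours whatever its causality (Section 12.6.3), and the contract research organisation decides SUSAR status. Serious TEAE rates are compared by arm regardless of relatedness, and laboratory shift tables are given by arm (Section 15.4). The DMC reviews accumulating data and receives unblinded outputs (Sections 15.8 and 9.3.2).

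A reader might infer that all three stopping rules are silenced. The text does not support that: rule 2 carries its own condition that no plausible alternative exists, so rewording Table 7 would not change it. Nor does the text support widespread conflict between unlikely and higher grades, since every such case needs a negative re-dosing.

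**Conclusion.** The point holds as an internal contradiction in Table 7 and a mismatch with Section 12.6.4. A new, well-timed event that the disease or standard of care could also explain meets 1 of 3 criteria for possibly and 2 of 4 for unlikely, in 6 of 6 combinations of stopping and re-dosing outcome. The overlap of unlikely with possibly is a corner case, 3 of 16.

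This rests on three assumptions: the investigator applies the listed criteria, regards the alternative as readily explaining the event, and sees no known pattern. Without a ready alternative, the same event reaches possibly. The documents do not say how often an alternative cause would be present, so the number of events affected cannot be estimated.

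It would go too far to conclude that drug harm will be missed. The supportable consequence is that the investigator's input to SUSAR decisions, stopping rules 1 and 3, and the treatment-related tables can be biased towards not related, with the safeguards above reducing the risk. The wording should be corrected.

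**What to change.** Reword Table 7 in both protocol versions and in the matching eCRF guidance.

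1. Make the criteria for unlikely and possibly agree with their descriptions and with Section 12.6.4. A well-timed event for which a drug cause cannot be excluded should be gradable as possibly even when the disease or standard of care could also explain it.
2. Do not let the absence of a known pattern push an event to unlikely. If that criterion no longer counted, the event in Step 1 would meet 1 unlikely criterion instead of 2, unless re-dosing was negative.
3. State that the higher grade takes precedence when two are met. This also settles the nested overlaps.
4. Reconcile the word related in Section 15.8 with the Table 7 grades, without prescribing a new stopping threshold. Simply declaring that possibly counts as related there would contradict rule 2's own condition and in effect create a new stopping rule, so it is not proposed.

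The change is to wording only. The cost is more events graded possibly related in both blinded arms and somewhat more expedited-report processing.
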